## 1. RCT Details

This section provides a high-level overview of a **published** RCT that the described real-world evidence study is trying to replicate as closely as possible given the remaining limitations inherent in the healthcare databases.

### 1.1 Title

**Effects of teriparatide and risedronate on new fractures in post-menopausal women with severe osteoporosis (VERO): a multicentre, double-blind, double-dummy, randomised controlled trial ([VERtebral fracture treatment comparisons in Osteoporotic women, VERO trial - NCT01709110](#))**

### 1.2 Intended aim(s)

To assess the effects of 24 months of treatment with teriparatide compared with risedronate on the incidence of new fractures in post-menopausal women with preexisting vertebral fractures, regardless of previous osteoporosis treatment.

### 1.3 Primary endpoint for replication

New vertebral fracture.

### 1.4 Required power for primary endpoint and noninferiority margin (if applicable)

Assuming a 24-month new vertebral fracture incidence of 4.5% in the teriparatide group and 10% in the risedronate group, 466 patients per group would provide 90% power to detect a difference between groups in the incidence of new vertebral fractures using a Pearson  $\chi^2$  test (two-sided  $\alpha$  of 0.05).

### 1.5 Secondary endpoint for replication (assay sensitivity) and RCT finding

Non-vertebral fracture.

### 1.6 Trial estimate

Hazard Ratio, HR = 0.44 (95% CI, 0.29 to 0.68) comparing teriparatide vs. risedronate group during a 24-month period (Kendler et al., 2007).

**2. Person responsible for implementation of replication in Aetion**

[name], MPH, implemented the study design in the Aetion Evidence Platform. She is not responsible for the validity of the design and analytic choices. All implementation steps are recorded, and the implementation history is archived in the platform.

[figure not shown]
**3. Data Source(s)**

Optum CDM, IBM® MarketScan®

**4. Study Design Diagram**

The study design diagram visualizes key aspects of the longitudinal study design for expedited review.

**Figure 1. Design Diagram – VERO TRIAL REPLICATION**

## 5. Cohort Identification

### 5.1 Cohort Summary

This study will involve a new user, parallel group, propensity score-matched, retrospective cohort design comparing injectable subcutaneous teriparatide (20 µg daily) to oral risedronate (35 mg weekly). The patients will be required to have continuous enrollment during a baseline period of 365 days before initiation of teriparatide or oral risedronate. We will restrict the analyses to women older than 45 with osteoporosis and history of vertebral fractures.

### 5.2 Important steps for cohort formation

New use of teriparatide (exposure) is defined as no use of the exposure drug within the 730 days (2 years) prior to index date. This will emulate the trial requirement for which treatment with teriparatide was not allowed any time before randomization. New use of risedronate (comparator) is defined as no use of the comparator drug within the 180 days prior to index date. The shorter washout period for risedronate users, compared to teriparatide users, will emulate the trial requirement of discontinuation of risedronate at the beginning of the screening period. Differently from teriparatide, history of risedronate use was allowed in the trial. New users of teriparatide are not allowed to receive risedronate within the 180 days prior to index date, and new users of risedronate are not allowed to receive teriparatide within the 730 days (2 years) prior to index date.

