#### 5.2.1 Eligible cohort entry dates

Teriparatide indication for treatment of osteoporosis in postmenopausal women was approved by FDA on Nov 26, 2002 (the approval of risedronate for the same indication was antecedent to 2002). The initial eligible cohort entry date was the first date after Nov 26, 2002 commonly available in both the databases investigated (IBM® MarketScan®, Optum CDM). The last date eligible as cohort entry date was the end of available data for IBM® MarketScan®. For Optum CDM, we excluded the data cut that overlaps with the COVID-19 pandemic (range: April 1st - Jun 30th, 2020), since we assumed a higher proportion of drug discontinuation in that time period. The following eligible cohort entry dates were included:

- IBM® MarketScan®: Jan 1, 2004 (start of available data) – December 31, 2018 (end of available data)
- Optum CDM: Jan 1, 2004 (start of available data) – Mar 31, 2020

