## 6. Variables

### 6.1 Exposure-related variables:

#### Study drug:

New initiation of injectable subcutaneous teriparatide (20 µg daily). New initiation is defined as no use of teriparatide in the prior 730 days before treatment initiation (washout period). New users of teriparatide are not allowed to receive risedronate within the 180 days prior to treatment initiation.

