#### Comparator agent:

New initiation of oral risedronate (35 mg weekly). New initiation is defined as no use of risedronate in the prior 180 days before treatment initiation (washout period). New users of risedronate are not allowed to receive teriparatide within the 730 days prior to treatment initiation.

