| 21.3 | Intravenous zoledronate, if the last dose was administered at least 12 months before Visit 1.   | 
Measured 365 days prior to and 1 day before the day of drug initiation:
 
Generic name:
Zoledronic Acid
   |  |
| 21.4 | Intravenous ibandronate or pamidronate, if the last dose was administered at least 3 months before Visit 1.   | 
Measured 90 days prior to and 1 day before the day of drug initiation:
 
Generic name:
Ibandronate or pamidronate
CPT codes:
C9229, J1740, C9411, J2430
  |  |
| 21.5 | Subcutaneous denosumab, if the last dose was administered at least 6 months before Visit 1.   | 
Measured 180 days prior to and 1 day before the day of drug initiation:
 
Generic name:
Denosumab
   |  |
| 21.6 | Fluoride unless given at therapeutic doses (> 20 mg/day) for more than 3 months in the 2 years prior to Visit 1, or for more than a total of 2 years, or at any dosages within the 6 months prior to Visit 2 (previous or current use of fluoridated water or topical dental fluoride treatment is permitted).    | N/A  | 
Sodium Fluoride is not used to treat the osteoporosis since 2001/2002 when a RCT and sub meta-analysis showed an increased of risk of fractures in the exp arm
  |
| 21.7 | Prior treatment with PTH, teriparatide, or other PTH analogs; or prior participation in any other clinical trial studying PTH, teriparatide, or other PTH analogs.  | 
Measured 730 days (2 years) prior to and 1 day before the day of drug initiation:
 
Generic names:
parathyroid hormone , teriparatide, abaloparatide
Brand names:
Abaloparatide (Reclast®), Teriparatide (Forteo®), Doseyab (Abaloparatide)
  |  |
| 22   | Known hypersensitivity to teriparatide or risedronate, or to any diluents or excipients of teriparatide or risedronate 35 mg/week oral tablet.  | N/A  |  |

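### The 730-day teriparatide-free rule is assured for only 365 days, and the osteoporosis criterion, read literally, lets every risedronate starter qualify on her index fill

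*Combined protocol and SAP*

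**What the plan says.** **Washout.** Section 5.2 sets the rule for the exposure arm: "New use of teriparatide (exposure) is defined as no use of the exposure drug within the 730 days (2 years) prior to index date". Section 6.1 repeats it under the study drug, "New initiation is defined as no use of teriparatide in the prior 730 days before treatment initiation (washout period", and under the comparator, "New users of risedronate are not allowed to receive teriparatide within the 730 days prior to treatment initiation". Appendix A, exclusion 21.7 (PTH, teriparatide and analogues), has the same window: "Measured 730 days (2 years) prior to and 1 day before the day of drug initiation". Section 5.2 explains that the two years stand in for the trial's bar on any teriparatide before randomisation.

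The only enrolment requirement is in Section 5.1, where patients are "required to have continuous enrollment during a baseline period of 365 days before initiation of teriparatide or oral risedronate". Section 5.2.1 gives, for both databases, "Jan 1, 2004 (start of available data" as the first eligible entry date, and notes that "Teriparatide indication for treatment of osteoporosis in postmenopausal women was approved by FDA on Nov 26, 2002".

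**Osteoporosis.** Section 5.1 applies the restriction to the whole cohort: "We will restrict the analyses to women older than 45 with osteoporosis and history of vertebral fractures". Appendix A, inclusion 3, implements it as a diagnosis or a listed treatment, measured from the start of the data up to and including the index day. Risedronate is on the treatment list and teriparatide is not. The Section 5.3 flowchart removes 3 women (Optum) and 18 (MarketScan) at this step, without a split by arm.

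**The concern.** A claims washout shows non-use only while the woman is observed. Where a woman has 365–729 observed days, the 730-day rule is met by default for the unobserved part. Readers will credit the cohort with a two-year teriparatide-free history that the design does not guarantee. A hidden prior user could sit in either arm: a returning user counted as a new user in one, or a woman with recent teriparatide exposure in the other.

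The second issue is an eligibility rule meant for both arms that may screen only one. A risedronate starter meets it through the prescription that brings her into the cohort. A teriparatide starter needs a diagnosis or another listed drug. Eligibility that depends on the assigned drug is a flaw in a comparative cohort even when few women are involved.

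**Working it through.** **Plan's own figure.** Section 10 reports pooled power 0.950 for 4,334 matched women, risk 17.80 per 1,000 and HR 0.44. With power = Φ(√events/2 × |ln HR| − 1.96):

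- events = 4,334 × 0.0178 = 77.1
- power = Φ(8.783/2 × 0.821 − 1.96) = Φ(1.645) = 0.950

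This reproduces. No stated power figure is in dispute.

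**(a) Look-back**

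1. Rule 730 days; enrolment 365 days; 730 − 365 = 365 days not assured. The 180-day risedronate washout lies inside the enrolled year and is unaffected.
2. If data start on Jan 1, 2004, the first woman with 365 observed days enters on Dec 31, 2004, and the first with 730 on Dec 31, 2005. The hidden in-window days fall in calendar 2003, after the approval date in Section 5.2.1, so on-label use was possible.
3. Matched Table 1 (Appendix B), 2004–2006 stratum: risedronate 44 + 150 = 194; teriparatide 43 + 149 = 192; total 386. 386/4,334 = 8.9%. This is a ceiling for the data-start route, because the stratum includes women entering from Dec 31, 2005 through 2006, who can have 730 days.
4. Entries were rising. Matched Optum: 87 in 2004–2006 (about 44 per year over the two years when entry was possible on this reading) and 245 in 2007–2009 (about 82 per year). MarketScan: 299 and 589 (about 150 and 196 per year). Half of the stratum, 193, is therefore probably too high an estimate.
5. Women entering later with 365–729 days of enrolment are not counted anywhere.
6. Criterion 20 in the flowchart removed 44 + 137 = 181 of 4,772 + 8,166 = 12,938 (1.4%) for recorded PTH or analogue use. This is what remained after the prior-exposure step had removed 19,897/81,878 = 24.3% and 44,254/172,846 = 25.6%. It also pools the arms: if all 181 were teriparatide starters, it is 181/(2,418 + 181) = 7.0% of that arm. It does not bound the unseen use.

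Power of an analysis restricted to 730 days, same formula, risk and HR:

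| Loss | Women | Events | Power |
|---|---|---|---|
| 2004–2006 stratum only | 3,948 | 70.3 | 0.931 |
| plus 10% of the rest | 3,553 | 63.2 | 0.904 |
| plus 20% | 3,158 | 56.2 | 0.868 |
| plus 30% | 2,764 | 49.2 | 0.821 |

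80% power needs 46.6 events, or 2,617 women, which is 34% below 3,948.

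**(b) Osteoporosis step**

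1. Final arms, summed from the unmatched age rows (risedronate/teriparatide): Optum 3,875/853, MarketScan 6,464/1,565.
2. Assume that this mix held at the osteoporosis step and that all 21 exclusions were teriparatide starters. Failure rates are then 3/(6,440 × 853/4,728) = 0.258% and 18/(11,270 × 1,565/8,029) = 0.819%.
3. Assume that risedronate women would fail at those rates: 747 × 0.258% + 1,420 × 0.819% = 13.6, about 14 of 2,167. With a teriparatide share of 10% at that step the figure is 26; with 30% it is 9.
4. Effect on the HR, taking equal follow-up. If the 14 had no events, dropping them gives 0.44 × 2,153/2,167 = 0.437. Expected risedronate events are 77.1/1.44 = 53.6. If one of the 14 had an event, the HR becomes 0.44 × (53.6/2,167)/(52.6/2,153) = about 0.445. The direction turns on a single event.

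**The case against.** On (a), the strongest reply is that this is an undisclosed limitation and not a contradiction. Section 5.2 never says that all 730 days are enrolled, and any finite look-back leaves earlier use unseen. That is fair as to wording, but the plan nowhere tells the reader that the second year may be unobserved.

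The data-start figure can also be challenged. Section 5.2.1 takes the first date common to both databases, so one source may hold earlier data. It also allows entry on Jan 1, 2004, when nobody could have 365 prior days if data truly began then. MarketScan supplies 299 of the 386 women, so the 8.9% leans on that label. This stands, and the figure is conditional on it. The gap between 365 and 730 days does not depend on it. The design diagram (Figure 1) was not available, so its windows were not checked.

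On (b), the index-day window is phrased for diagnoses, and no separate window is given for treatments. Most drug look-backs in Appendix A end the day before index, and Appendix A refers to external files for further detail. The implementation may therefore differ from the literal text. Every woman also already has a vertebral-fracture code or procedure, and code 733.13 and M80 codes appear in both lists, so most would qualify anyway. Both points stand. They limit the size but do not remove the asymmetry in the text.

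A reader might infer more: that 8.9% of women are misclassified, that the result is biased in a known direction, or that the 21 exclusions are proven to be teriparatide starters. The documents support none of these. Short look-back is not prior use, the matched stratum is balanced (194 and 192), and the flowchart is not split by arm. Nor do they prove that the misclassification in (a) is negligible.

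**Conclusion.** Both points hold as minor design defects.

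(a) The assured teriparatide washout is 365 days in both arms, against a stated 730. On the data-start route at most 386 of 4,334 matched women (8.9%) have a short look-back, provided that data begin on Jan 1, 2004. Later entrants with short enrolment, the number of hidden prior users and the direction of any bias cannot be determined from the documents.

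(b) Read literally, the osteoporosis criterion cannot exclude a risedronate starter, and on that reading the 21 exclusions fall on teriparatide starters. The effect is probably small: about 14 matched risedronate women (9 to 26). This assumes that they would fail at the teriparatide rate, which cannot be observed under the present rule. The direction of any change in the HR is unknown.

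**What to change.** **(a)** Keep the 365-day primary cohort. State in Sections 5.2 and 6.1 that the assured teriparatide washout is 365 days. Report by arm the number with under 730 days of prior enrolment. Add a sensitivity analysis restricted to at least 730 days. The cost is one text change, one count and one analysis. The power of that analysis depends on a further loss that only the count will show.

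**(b)** End the osteoporosis-treatment look-back the day before index in both arms, so that the index fill does not count, and leave the diagnosis look-back as it is. Exclusions 21.2–21.5 already end the day before. Report exclusions at this step by arm.

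If the cohort is rebuilt before Section 13 is run, apply this in the primary analysis. The cost is new matches, Table 1 and power tables, a repeat of the Section 10 review (dated 04/15–16/2021) and an update to the document registered on 04/30/2021. Pooled power stays near 0.949 (4,306 women, 76.6 events), or 0.948 if 26 pairs are lost. For perhaps 14 women a rebuild for this reason alone is hard to justify. Otherwise, run a sensitivity analysis that drops risedronate women who qualify only on the index fill.

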#### 5.2.1 Eligible cohort entry dates

Teriparatide indication for treatment of osteoporosis in postmenopausal women was approved by FDA on Nov 26, 2002 (the approval of risedronate for the same indication was antecedent to 2002). The initial eligible cohort entry date was the first date after Nov 26, 2002 commonly available in both the databases investigated (IBM® MarketScan®, Optum CDM). The last date eligible as cohort entry date was the end of available data for IBM® MarketScan®. For Optum CDM, we excluded the data cut that overlaps with the COVID-19 pandemic (range: April 1st - Jun 30th, 2020), since we assumed a higher proportion of drug discontinuation in that time period. The following eligible cohort entry dates were included:

- IBM® MarketScan®: Jan 1, 2004 (start of available data) – December 31, 2018 (end of available data)
- Optum CDM: Jan 1, 2004 (start of available data) – Mar 31, 2020

#### 5.2.2 Specify inclusion/exclusion criteria for cohort entry and define the index date

Inclusion and exclusion criteria were adapted from the trial as closely as possible. Definitions for all inclusion/exclusion are provided in **Appendix A** and are summarized in the flowcharts below.

### 5.3 Flowchart of the study cohort assembly

For teriparatide vs. risedronate

|  | Optum CDM         |                    | IBM® MarketScan®  |                    |
|--|-------------------|--------------------|-------------------|--------------------|
|  | Excluded Patients | Remaining Patients | Excluded Patients | Remaining Patients |
| All patients   |                   | 78202636           |                   | 200203908          |
| Did not meet cohort entry criteria   | -77830806         | 371830             | -199450502        | 753406             |
| Excluded due to insufficient enrollment  | -90897            | 280933             | -176733           | 576673             |
| Excluded due to prior use of referent  | -199055           | 81878              | -403827           | 172846             |
| Excluded due to prior use of exposure  | -19897            | 61981              | -44254            | 128592             |
| Excluded because patient qualified in >1 exposure category   | 0                 | 61981              | 0                 | 128592             |
| Excluded based on Inclusion criteria #1 - Age >= 45  | -1814             | 60167              | -3865             | 124727             |
| Excluded based on Inclusion criteria #2 - Female   | -4439             | 55728              | -9140             | 115587             |
| Excluded based on Inclusion criteria #3.1 - History of vertebral fracture (including from inception to 90 days)      | -48548            | 7180               | -103348           | 12239              |
| Excluded based on Inclusion criteria #3.2 - Vertebral fracture diagnosis excluded in the 90 days before cohort entry | -740              | 6440               | -969              | 11270              |
| Excluded based on Inclusion criteria #4 - Osteoporosis   | -3                | 6437               | -18               | 11252              |
| Excluded based on Exclusion criteria #1 - Pregnancy  | -1                | 6436               | -1                | 11251              |
| Excluded based on Exclusion criteria #2 - Paget's Disease  | -5                | 6431               | -9                | 11242              |
| Excluded based on Exclusion criteria #3.1 - Renal Osteodystrophy   | -2                | 6429               | -1                | 11241              |
| Excluded based on Exclusion criteria #3.2 - Osteomalacia   | -11               | 6418               | -12               | 11229              |
| Excluded based on Exclusion criteria #3.3 - Cushing syndrome and other disorders of adrenal glands                   | -35               | 6383               | -62               | 11167              |
| Excluded based on Exclusion criteria #3.4 - Hyperparathyroidism and hypoparathyroidism                               | -60               | 6323               | -86               | 11081              |
| Excluded based on Exclusion criteria #3.5 - Intestinal malabsorption   | -27               | 6296               | -41               | 11040              |
| Excluded based on Exclusion criteria #4 - Hypercalcemia and Hypocalcemia   | -14               | 6282               | -23               | 11017              |
| Excluded based on Exclusion criteria #5 - Malignant neoplasm, excluding non-melanoma skin cancer                     | -500              | 5782               | -936              | 10081              |
| Excluded based on Exclusion criteria #6 - End-stage liver disease (ESLD)   | -31               | 5751               | -51               | 10030              |
| Excluded based on Exclusion criteria #7 - End-stage renal disease (ESRD)   | -6                | 5745               | -14               | 10016              |
| Excluded based on Exclusion criteria #8 - Nephrolithiasis or urolithiasis  | -52               | 5693               | -109              | 9907               |
| Excluded based on Exclusion criteria #9 - Kyphoplasty or vertebroplasty  | -17               | 5676               | -47               | 9860               |

|   |      |             |       |             |
|---|------|-------------|-------|-------------|
| Excluded based on Exclusion criteria #10 - Osteonecrosis of the jaw                                 | 0    | 5676        | -2    | 9858        |
| Excluded based on Exclusion criteria #11 - Atypical subtrochanteric or diaphyseal femoral fractures | -28  | 5648        | -55   | 9803        |
| Excluded based on Exclusion criteria #12 - Upper gastrointestinal disorders                         | -170 | 5478        | -221  | 9582        |
| Excluded based on Exclusion criteria #13 - CCI (180 days)   | -2   | 5476        | -1    | 9581        |
| Excluded based on Exclusion criteria #14 - Drug addiction or alcohol abuse or not compliant         | -91  | 5385        | -58   | 9523        |
| Excluded based on Exclusion criteria #15 - Oral bisphosphonate use                                  | -499 | 4886        | -1024 | 8499        |
| Excluded based on Exclusion criteria #16 - SERMs, Calcitonin, HRT                                   | -101 | 4785        | -321  | 8178        |
| Excluded based on Exclusion criteria #17 - Zoledronic acid use                                      | -2   | 4783        | -7    | 8171        |
| Excluded based on Exclusion criteria #18 - Intravenous ibandronate or pamidronate                   | -1   | 4782        | -1    | 8170        |
| Excluded based on Exclusion criteria #19 - Denosumab use  | -10  | 4772        | -4    | 8166        |
| Excluded based on Exclusion criteria #20 - PTH or PTH analogue use                                  | -44  | 4728        | -137  | 8029        |
| Excluded based on Exclusion criteria #21 - Romosozumab  | 0    | 4728        | 0     | 8029        |
| Final cohort  |      | 4728 |       | 8029 |

## 6. Variables

### 6.1 Exposure-related variables:

#### Study drug:

New initiation of injectable subcutaneous teriparatide (20 µg daily). New initiation is defined as no use of teriparatide in the prior 730 days before treatment initiation (washout period). New users of teriparatide are not allowed to receive risedronate within the 180 days prior to treatment initiation.

